### **3.4. Examination of Subject Subgroups**

There are no pre-specified subject subsets for efficacy or safety analyses.

### **3.5. Multiple Comparisons**

All endpoint tests will be done at the significance level of 0.05 with no multiplicity adjustment in this proof-of-concept study.

### **3.6. Missing Data and Outliers**

#### **3.6.1. Missing Data**

A missing datum for a given study analysis window may be due to any of the following reasons:

- A visit occurring in the window but data were not collected or were unusable
- A visit not occurring in the window
- A subject prematurely discontinuing from the study before reaching the window

In general, values for missing data will not be imputed, unless methods for handling missing data are specified.

The handling of missing or incomplete dates for AE onset is described in Section 7.1.6.2, and for concomitant medications in Section 7.4.

#### **3.6.2. Outliers**

Outliers will be identified during the data management and data analysis process, but no sensitivity analyses will be conducted to evaluate the impact of outliers on efficacy or safety outcomes, unless specified otherwise. All data will be included in the data analyses.

### **3.7. Data Handling Conventions and Transformations**

Laboratory data that are continuous in nature but are less than the lower limit of quantitation (LLOQ) or above the upper limit of quantitation (ULOQ) will be imputed as follows except for urine creatinine:

- A value that is 1 unit less than the limit of quantitation (LOQ) will be used to calculate descriptive statistics if the datum is reported in the form of “< x” (where x is considered the LOQ). For example, if the values are reported as < 50 and < 5.0, values of 49 and 4.9, respectively, will be used to calculate summary statistics. An exception to this rule is any value reported as < 1 or < 0.1, etc. For values reported as < 1 or < 0.1, a value of 0.9 or 0.09, respectively, will be used to calculate summary statistics.
- A value that is 1 unit above the LOQ will be used to calculate descriptive statistics if the datum is reported in the form of “> x” (where x is considered the LOQ). Values with decimal points will follow the same logic as above.
- The LOQ will be used to calculate descriptive statistics if the datum is reported in the form of “≤ x” or “≥ x” (where x is considered the LOQ).

For urine creatinine, a value of “< 1” is handled as a missing value in its summary and the calculation of related ratios.

Logarithmic (base 10) transformations will be applied to HIV-1 RNA data for efficacy analyses. HIV-1 RNA results of ‘No HIV-1 RNA detected’ and “< 20 cp/mL HIV-1 RNA Detected” will be imputed as 19 copies/mL for analysis purposes.

Biomarker values that are below the limit of quantitation (BLQ) will be presented as “BLQ” in the data listing. Values that are BLQ will be treated as LLOQ at both predose and postbaseline time points.

Natural logarithm transformation will be used for plasma/blood concentrations and analysis of PK parameters. Plasma concentration values that are below BLQ will be presented as “BLQ” in the concentration data listing. Values that are BLQ will be treated as 0 at pre-dose time points, and one-half the value of the LLOQ at postbaseline time points.

The following conventions will be used for the presentation of summary and order statistics:

- If at least 1 subject has a concentration value of BLQ for the time point, the minimum value will be displayed as “BLQ.”
- If more than 25% of the subjects have a concentration data value of BLQ for a given time point, the minimum and Q1 values will be displayed as “BLQ.”
- If more than 50% of the subjects have a concentration data value of BLQ for a given time point, the minimum, Q1, and median values will be displayed as “BLQ.”
- If more than 75% of the subjects have a concentration data value of BLQ for a given time point, the minimum, Q1, median, and Q3 values will be displayed as “BLQ.”
- If all subjects have concentration data values of BLQ for a given time point, all order statistics (minimum, Q1, median, Q3, and maximum) will be displayed as “BLQ.”

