1.2.3.1. GS-US-243-0101

Study GS-US-243-0101 was a first-in-human, randomized, double-blind, placebo-controlled, single ascending dose (SAD) study of GS-9620 in 75 healthy male and female subjects. The primary objective of the study was to evaluate the safety and tolerability of GS-9620 and the secondary objectives were to characterize the plasma PK/PD profile of GS-9620. Doses used were: 0.3, 1, 2, 4, 6, 8, and 12 mg.

The treatment was generally well tolerated. There were no Grade 4 AEs or serious adverse events (SAEs) reported, and most AEs were mild. No individual subject discontinued due to AEs or laboratory abnormalities. Treatment-emergent Grade 3 AEs included pyrexia in 2 subjects who received GS-9620 12 mg. A higher incidence of flu-like symptoms was also reported in subjects administered the higher doses (8 and 12 mg). Myalgia and headache were reported by subjects in both the 8 and 12 mg cohorts, while pyrexia and chills were only reported by subjects in the 12 mg cohort.

Plasma concentrations of GS-9620 peaked between 1.5 and 6 hours after dosing and declined gradually over 48 hours. The mean maximum plasma concentration (C_{max}) ranged from 184.2 pg/mL at the 0.3 mg dose to 11.97 ng/mL at the 12 mg dose. Exposures were higher in the fasted state than in the fed state. After the 1 mg, 2 mg, and 4 mg doses, GS-9620 was detectable at 48 hours after dosing and had a median terminal half-life between 17.16 and 26.96 hours.

Three ISGs were analyzed: ISG15, MX-1 and OAS-1. Significant ISG induction was observed at the 2-mg dose and above. ISG15 mRNA expression showed the highest induction compared to MX-1 and OAS-1. Serum IFN- α was detected transiently in subjects who received the 8 or 12 mg doses, and only the 12 mg cohort had a >2-fold mean change in serum IFN- α from baseline. A dose-dependent induction was observed for serum IP-10 but not for IFN- α or TNF- α . Dose-dependent T cell activation was also observed at the 2 mg dose and above.

In summary, single doses of GS-9620 up to 12 mg were well tolerated, with significant ISG induction and T cell activation at doses of 2, 4, and 6 mg in the absence of detectable serum IFN- α or systemic AEs.

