### **3. GENERAL CONSIDERATIONS FOR DATA ANALYSES**

Analysis results will be presented using descriptive statistics. For categorical variables, the number and percentage of subjects in each category will be presented; for continuous variables, the number of subjects (n), mean, standard deviation (SD) or standard error (SE), median, first quartile (Q1), third quartile (Q3), minimum, and maximum will be presented.

All statistical tests will be 2-sided and performed at the 5% significance level unless otherwise specified.

By-subject listings will be presented for all subjects in the All Randomized Analysis Set and sorted by subject ID number, visit date, and time (if applicable), unless specified otherwise. Data collected on log forms, such as AEs, will be presented in chronological order within the subject. The treatment group to which subjects were randomized will be used in the listings. Age, sex at birth, race, and ethnicity will be included in the listings, as space permits.

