### **3.8.3. Selection of Data in the Event of Multiple Records in a Window**

Depending on the statistical analysis method, single values may be required for each day. For example, change from baseline by visit usually requires a single value.

If multiple valid, nonmissing, numeric measurements exist on the same nominal visit, records will be chosen based on the following rules if a single value is needed:

- In general, the baseline value will be the last nonmissing value on or prior to the first dosing date of study drug, unless specified differently. If multiple measurements occur on the same day, the last nonmissing value prior to the time of first dosing of study drug will be considered as the baseline value. If these multiple measurements occur at the same time or the time is not available, the average (arithmetic or geometric mean, as appropriate) of these measurements (for continuous data) will be considered the baseline value.
- For postbaseline values:
  - If there is more than one record on the selected day, the average will be taken (geometric mean for HIV-1 RNA and arithmetic mean for others), unless otherwise specified.

If multiple valid, nonmissing, categorical measurements exist on the same nominal visit, records will be chosen based on the following rule if a single value if needed:

- For baseline, the last available record on or prior to the first dose of study drug will be selected. If there are multiple records with the same time or no time recorded on the same day, the value with the lowest severity will be selected (eg, normal will be selected over abnormal for safety ECG findings).
- For postbaseline visits, the value for the scheduled visit only will be used. If multiple records are available for a scheduled visit, the most conservative value within that day will be selected (eg, abnormal will be selected over normal for safety ECGs).

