### **6.3. Other Efficacy Analyses**

#### **6.3.1. Definition of the Other Efficacy Endpoints**

Other efficacy endpoints include the following:

- Change, percentage change and fold change from baseline in the levels of serum cytokines (including IFN- $\alpha$ , IL-1RA, IP-10, and ITAC)
- Fold change in mRNA for ISGs including MX1, OAS1 and ISG15
- Change and percentage change from baseline in CD4/CD38/HLADR, CD8/CD38/HLADR and NK cell activation

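### ISG and cytokine fold changes are to be summarised by an arithmetic mean of raw ratios, which sits above 1-fold in expectation even with no drug effect; a geometric mean would correct this at almost no cost.

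*SAP*

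**What the plan says.** SAP 3.7 sets the scale for two kinds of data. Base-10 logarithmic "transformations will be applied to HIV-1 RNA data for efficacy analyses", and "Natural logarithm transformation will be used for plasma/blood concentrations and analysis of PK parameters". For biomarkers it gives only a rule for values below the limit of quantitation (BLQ): "Values that are BLQ will be treated as LLOQ at both predose and postbaseline time points". The PK sentence does not cover the cytokines, which are serum biomarkers with this BLQ rule of their own.

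SAP 6.3.1 lists "Change, percentage change and fold change from baseline in the levels of serum cytokines" and "Fold change in mRNA for ISGs including MX1, OAS1 and ISG15". ISGs therefore have fold change only, and cytokines have all three measures. SAP 6.3.2 defines fold change as postbaseline divided by baseline, summarises it with descriptive statistics, and compares each dose group with pooled placebo by a two-sided Wilcoxon rank sum test at 0.05.

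SAP 3 defines the descriptive statistics for continuous variables: besides n, the "mean, standard deviation (SD) or standard error (SE), median, first quartile (Q1), third quartile (Q3), minimum, and maximum will be presented". No geometric mean is among them. SAP 8.3.1 does give a geometric mean with 95% CI, but only for PK parameters.

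**The concern.** A ratio is asymmetric about 1. A 4-fold rise is +300%, while a 4-fold fall is only −75%, so pure noise averages to an apparent increase. The SAP avoids this for HIV-1 RNA and PK by working on the log scale, but it leaves out the biomarkers, where fold change is the stated measure.

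ISG and cytokine responses serve a secondary objective (SAP 1.1). If a table shows a mean fold change above 1 in a group of six, a reader may take it as induction although part or all of it comes from the scale. The effect is largest for the most variable analytes.

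**Working it through.** **Inputs.** Six active subjects per cohort (SAP 1.2). Pooled placebo of 6 cohorts × 2 = 12 (SAP 1.2 and 3.2). Fold change is the raw ratio (SAP 6.3.2). The documents give no biomarker variability and no figure to reproduce, so the within-subject CV at each time point is an assumption, shown over a range.

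**Toy case.** Take the ratios 0.25, 0.5, 1, 1, 2, 4, which are symmetric on the log scale. The arithmetic mean is 8.75/6 = 1.46. The median and the geometric mean are both 1.00.

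**Expected mean with no effect.** Let baseline and postbaseline carry independent log-normal variation with log-scale variance ln(1 + CV²). The log ratio is then normal with mean 0 and variance s² = 2·ln(1 + CV²), and

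E[ratio] = exp(s²/2) = 1 + CV².

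The corresponding expected mean percentage change is 100 × CV². Simulation (200,000 trials, n = 6) agrees with the formula:

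| Assumed CV | Expected mean fold | Expected mean % change | Chance that a mean of 6 exceeds 1 | Chance that a median of 6 exceeds 1 | Chance that a geometric mean of 6 exceeds 1 |
|---|---|---|---|---|---|
| 30% | 1.09 | +9% | 0.66 | 0.51 | 0.50 |
| 50% | 1.25 | +25% | 0.73 | 0.52 | 0.50 |
| 100% | 2.00 | +100% | 0.82 | 0.53 | 0.50 |

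A group mean above 1 is thus likely but not certain. In groups of six the alternatives also lean up slightly when averaged over repeated trials. At CV 50% the average geometric mean is 1.04 and the average median 1.07; at CV 100% they are 1.12 and 1.22.

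**Comparison with placebo.** The same formula applies to the 12 placebo subjects, so the expected active-minus-placebo difference in means is 0 (simulated differences between −0.001 and 0.003).

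**Rank test.** The Wilcoxon test uses only order. Log ratio and percentage change are both increasing functions of fold change, the latter being 100 × (fold − 1). In 2,000 simulated comparisons of 6 with 12, the p-values on the ratio, log and percentage scales were identical every time. The null rejection rate was 0.045 (20,000 trials).

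**Effect of the BLQ rule.** If both values are BLQ, the ratio is exactly 1. In an illustrative case with a between-subject log SD of 0.8 and a within-subject log SD of 0.4, the null mean falls from 1.17 uncensored to 1.07, 1.03 and 1.01 with 50%, 80% and 90% BLQ. With the same between-subject SD and 80% BLQ, it is 1.04, 1.06 and 1.10 at CV 50%, 70% and 100%.

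**The case against.** The strongest reply is that the plan already protects the comparison it cares about. The pharmacodynamic objective is change compared with placebo, the test is rank-based, placebo shares the expected bias, and the median and quartiles are tabulated beside the mean. The endpoints are classed as other efficacy endpoints, in an exploratory study with no power calculation. All of this stands, and it keeps the point to one summary statistic.

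Several stronger readings are tempting, and the documents do not support them.

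- A reader might infer that a 2-fold mean is this trial's mark of activity, because Protocol 1.2.3.1 says that "only the 12 mg cohort had a >2-fold mean change in serum" IFN-α. That sentence describes an earlier single-dose study in healthy subjects and does not say which kind of mean was used. Neither document sets a fold threshold here. Without censoring, the chance that a null mean of six exceeds 2-fold is about 0.02%, 4%, 17% and 37% at CV 30%, 50%, 70% and 100%. With 80% BLQ (between-subject log SD 0.8) it is about 0.05%, 0.5% and 2% at CV 50%, 70% and 100%. The BLQ case is relevant to IFN-α, which Protocol 1.4 reports as undetectable in most of the hepatitis patients.
- A reader might infer that testing both fold and percentage change for cytokines inflates the error rate. The second test repeats the first exactly, so it adds a redundant row and no extra false positives.
- A reader might extend the point to same-day records, which SAP 3.8.3 averages by "geometric mean for HIV-1 RNA and arithmetic mean for others". The assessment schedules show one collection per visit for these analytes, so no practical consequence is shown. Nor has any bias in the SDs been shown.

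**Conclusion.** The point holds as a low-severity reporting matter. No log transformation or geometric mean is stated for ISG and cytokine fold changes, and the planned arithmetic mean of ratios has expectation 1 + CV² under no effect. That rests on independent log-normal variation of equal CV at both time points and on an assumed CV. The true size cannot be known from the documents, and for mostly-BLQ analytes it is small.

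The error arises only when a dose group's mean is read against 1-fold (or 0%) without its median or the placebo column. It does not affect the Wilcoxon p-values, and it gives no reason to expect the trial to declare activity falsely.

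**What to change.** In SAP 6.3.2, report ISG and cytokine fold change as the geometric mean (the back-transformed mean log2 ratio) with its 95% CI, beside the median and quartiles and in place of the arithmetic mean of ratios. State the log2 scale for these analytes in SAP 3.7. SAP 8.3.1 already provides the same type of summary for PK parameters.

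Report cytokine percentage change descriptively only and drop its rank test. Its mean carries the same upward bias, so its median is the figure to read.

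The cost is a few lines of SAP text and a changed summary statistic, with no new data and no change to the remaining tests. Reported mean inductions will be somewhat smaller. The change should be made before the final unblinding, so that the headline summary is not chosen after the results are seen.

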### **3.8. Analysis Visit Windows**

#### **3.8.1. Definition of Study Day**

Study day will be calculated from the first dosing date of study drug and derived as follows:

- For postdose study days: Assessment Date – First Dosing Date + 1
- For days prior to the first dose: Assessment Date – First Dosing Date

Therefore, study day 1 is the day of first dose of study drug administration.

### **3.8.2. Analysis Visit Windows**

The nominal visit as recorded on the CRF or lab date will be used when data are summarized by visit. Any data relating to unscheduled visits will not be assigned to a particular visit or time point and will not be included in the summary tables, but will be included in the listings. However, the following exceptions will be made:

- An unscheduled visit prior to the first dosing of study drug may be included in the calculation of the baseline value, if applicable.
- Unscheduled visits after the first dose of study drug will be included in determining the maximum postbaseline toxicity grade.
- For subjects who prematurely discontinue from the study, early termination (ET) data will be summarized as a separate visit, labeled as “Early Termination Visit”.
- Data obtained after the follow-up visit or last dose date plus 30 days (whichever is later) will be excluded from the summaries, but will be included in the listings.

### **3.8.3. Selection of Data in the Event of Multiple Records in a Window**

Depending on the statistical analysis method, single values may be required for each day. For example, change from baseline by visit usually requires a single value.

If multiple valid, nonmissing, numeric measurements exist on the same nominal visit, records will be chosen based on the following rules if a single value is needed:

- In general, the baseline value will be the last nonmissing value on or prior to the first dosing date of study drug, unless specified differently. If multiple measurements occur on the same day, the last nonmissing value prior to the time of first dosing of study drug will be considered as the baseline value. If these multiple measurements occur at the same time or the time is not available, the average (arithmetic or geometric mean, as appropriate) of these measurements (for continuous data) will be considered the baseline value.
- For postbaseline values:
  - If there is more than one record on the selected day, the average will be taken (geometric mean for HIV-1 RNA and arithmetic mean for others), unless otherwise specified.

If multiple valid, nonmissing, categorical measurements exist on the same nominal visit, records will be chosen based on the following rule if a single value if needed:

- For baseline, the last available record on or prior to the first dose of study drug will be selected. If there are multiple records with the same time or no time recorded on the same day, the value with the lowest severity will be selected (eg, normal will be selected over abnormal for safety ECG findings).
- For postbaseline visits, the value for the scheduled visit only will be used. If multiple records are available for a scheduled visit, the most conservative value within that day will be selected (eg, abnormal will be selected over normal for safety ECGs).

## **4. SUBJECT DISPOSITION**

### **4.1. Subject Enrollment and Disposition**

#### **4.1.1. Subject Enrollment**

A summary of subject enrollment will be provided by treatment group for each country, investigator within a country and overall for all cohorts combined. The summary will present the number and percentage of subjects enrolled. The denominator for the percentage calculation will be the total number of enrolled subjects for that column.

The randomization schedule used for the study will be provided as an appendix to the clinical CSR.

#### **4.1.2. Subject Disposition**

The summary of subject disposition will be provided by treatment group and overall for all screened subjects for all cohorts combined. This summary will include the number of subjects screened, screen failure subjects who were not randomized, subjects who met all eligibility criteria and were not randomized, subjects randomized, subjects randomized but never treated, subjects in the safety analysis set, and subjects in the FAS.

In addition, the number and percentage of the subjects in the following categories will be summarized:

- 1) Completed study drug
- 2) Prematurely discontinuing study drug (with summary of reasons for discontinuing study drug)
- 3) Completed the study
- 4) Prematurely discontinuing from study (with summary of reasons for discontinuing study).

The denominator for the percentages of subjects in each category will be the number of subjects in the safety analysis set.

No inferential statistics will be generated. A data listing of reasons for premature study drug/study discontinuation will be provided.

### **4.2. Extent of Exposure**

A subject's extent of exposure to study drug data will be generated from the study drug administration page in the eCRF. Exposure data will be listed.

### **4.3. Protocol Deviations**

Protocol deviations occurring after subjects entered the study are documented during routine monitoring. The number and percentage of subjects with important protocol deviations by deviation reason and the total number of important protocol deviations by deviation reason (eg, nonadherence to study drug, violation of select inclusion/exclusion criteria) will be summarized by treatment group for the Full Analysis Set. A by-subject listing will be provided for those subjects with important protocol deviation.

## 5. BASELINE CHARACTERISTICS

### 5.1. Demographics and Baseline Characteristics

Subject demographic data (eg, age, sex at birth, race, and ethnicity) and baseline characteristics (eg, body weight, height, and body mass index [BMI]) will be summarized by treatment group and overall for all cohorts combined using descriptive statistics (n, mean, SD, median, Q1, Q3, minimum, and maximum) for continuous data and by the number and percentage of subjects for categorical data. The summaries of demographic data and baseline subject characteristics will be provided for the safety analysis set.

### 5.2. Baseline Disease Characteristics

The following baseline disease characteristics will be summarized:

- HIV-1 RNA ( $\log_{10}$  copies/mL)
- HIV-1 RNA categories (copies/mL) (a)  $< 50$  and (b)  $\geq 50$
- CD4 cell count (/ $\mu\text{L}$ )
- CD4+ cell count categories (/ $\mu\text{L}$ ): (a)  $< 50$ , (b)  $\geq 50$  to  $< 200$ , (c)  $\geq 200$  to  $< 350$ , (d)  $\geq 350$  to  $< 500$ , and (e)  $\geq 500$
- CD4 percentage (%)
- eGFRCG (mL/min)
- Mode of infection (HIV risk factors)
- HIV disease status
- Duration of being diagnosed with HIV disease (in years)
- Duration of ARV prior to study (in years)
- Pre-ARV HIV-RNA viral set point ( $\log_{10}$  copies/mL)
- Pre-ARV HIV-RNA categories (copies/mL): (a)  $\leq 100,000$ , (b)  $> 100,000$  to  $\leq 400,000$ , and (c)  $> 400,000$
- Pre-ARV CD4 cell count (/ $\mu\text{L}$ )
- Pre-ARV CD4 cell count categories (/ $\mu\text{L}$ ): (a)  $< 50$ , (b)  $\geq 50$  to  $< 200$ , (c)  $\geq 200$  to  $< 350$ , (d)  $\geq 350$  to  $< 500$ , and (e)  $\geq 500$

